2 INTRODUCTION

Product description

Brivaracetam ((2S)-2-[(4R)-2-oxo-4-propyltetrahydro-1*H*-pyrrol-1-yl] butanamide) is a 2-pyrrolidone derivative. The current targeted therapeutic indications for BRV in Japan are monotherapy and adjunctive therapy in the treatment of focal/partial-onset seizures (POS) with or without secondary generalization in patients from 4 years of age with epilepsy.

Brivaracetam displays a high and selective affinity for the synaptic vesicle protein 2A (SV2A) in the brain. Binding to SV2A is believed to be the primary mechanism for BRV anticonvulsant activity (Matagne et al, 2008).

More detailed information regarding the nonclinical and clinical development programs for BRV, including all completed and ongoing studies, can be found in the latest version of the Investigator's Brochure (IB).

Pharmacokinetics

Brivaracetam is rapidly and completely absorbed throughout the gastrointestinal tract. The median t_{max} is 1hr (range: 0.25 to 3hr) after dosing in fasting participants. The pharmacokinetics (PK) of BRV is dose proportional from 10mg to at least 600mg (for single dose). A food-effect study involving administration of BRV to healthy participants under fasting conditions and with a high-fat, high-calorie meal indicated that under fed conditions the C_{max} was decreased by 28% and t_{max} occurred 3hr later, while the AUC remained unchanged. The decrease in absorption rate is not clinically significant; therefore, BRV can be taken without regards to meals.

Brivaracetam follows single-compartment first-order PK, without an apparent distribution phase. The volume of distribution is 0.5L/kg, a value that is close to the volume of total body water. Brivaracetam is weakly bound to plasma proteins (<20%). The plasma half-life of BRV is approximately 9hr in healthy adults. More than 95% of the dose, including less than 9% as unchanged BRV, is excreted in the urine within 72hr after dosing. Fecal and expired air excretion account for <1% of the dose.

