9.5 Handling of protocol deviations

All protocol deviations will be reviewed on an ongoing basis as part of the data cleaning and evaluation process. After all data have been verified/entered into the database, and prior to database lock, a Data Evaluation Meeting will be performed for each cohort. The purpose of this review meeting will be to examine all protocol deviations, define the PKS (Section 9.1), and to verify the quality of the data. If PK parameters are needed to define the PKS, it will be performed based on the analysis data set of the pharmacokinetic parameters. The data evaluation will also help in guiding decisions on how to manage data issues on a case-by-case basis (eg, missing values, dropouts, and protocol deviations).

Accepted deviations from theoretical time points will be described in the appropriate documents and included in the electronic Trial Master File. After the data review, resolution of all issues, and documentation of all decisions, the database will be locked.

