9.6 Handling of dropouts or missing data

Handling of missing data will be detailed in the SAP.

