## 1.2 Study design

EP0231 is a single-center, multiple-dose, open-label, randomized, group sequential design, 2-way cross-over study to assess the bioequivalence of BRV 50mg tablet and BRV 50mg dry syrup in healthy male Japanese participants after oral administration under fasted conditions. In addition, the safety and tolerability of BRV will be evaluated.

[figure not shown]
Participants will enter a Screening Period (2 to 28 days before administration of investigational medicinal product [IMP]), and eligible participants will start the Dosing Period. The Dosing Period consists of 2 periods (Dosing Period 1 and Dosing Period 2) of 5 days each (Day -1 to Day 4) with a total of 5 administrations of BRV 50mg on Day 1 and Day 2 (morning and evening doses 12 hours apart), and Day 3 (morning dose only).

Participants will receive 1 of the following treatments in each Dosing Period under fasting conditions according to randomly assigned treatment sequences (A-B or B-A):

- Treatment A – multiple doses of BRV 50mg tablets
- Treatment B – multiple doses of BRV 50mg dry syrup (1.25g of granules for oral suspension 4% w/w)

The Dosing Periods will be separated by a Wash-Out Period (minimum of 6 days and preferably no more than 10 days between the final dose in Dosing Period 1 and the first dose in Dosing Period 2 for each participant) and followed by a Safety Follow-Up (SFU) Visit, 7 to 9 days after the last administration of IMP. Participants who prematurely discontinue the IMP/study will be encouraged to return for an SFU Visit, 7 to 9 days after the final IMP administration. Refer to the study schematic in [Figure 1-1](#).

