### 3.4 Pharmacokinetic Set

The Pharmacokinetic Set (PKS) consists of all study participants who are randomized, receive at least 1 dose of active IMP and have at least 1 quantifiable post-Baseline PK measurement.

All PKS participants who have a sufficient number of bioanalytical assessments to calculate reliable estimates for the primary PK parameters for both BRV formulations will be included in the statistical analysis.

If a participant's predose concentration on Day 1 is greater than 5% of the  $C_{max,ss}$  value on Day 3 in a Dosing Period, the participant's data from that Dosing Period will be excluded from the statistical analysis. If a participant's predose concentration on Day 1 is greater than 5% of the  $C_{max,ss}$  value on Day 3 for both Dosing Periods, the participant will be excluded from the statistical analysis.

If vomiting occurs at or before 2 times the median  $t_{max,ss}$  for the tablet and the dry syrup within a Dosing Period, the participant's data from that period will be excluded from the statistical analysis. If vomiting occurs at or before 2 times the median  $t_{max,ss}$  within a Dosing Period, for both Dosing Periods, the participant will be excluded from the statistical analysis.

If (1) a PK sample is missing and the  $C_{max,ss}$  is the sample immediately preceding or following the missing sample or (2) 2 or more samples are missing, then the participant's data from that period will be excluded from the statistical analysis.

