#### 4.6.1.1.1 Plasma concentration-time profiles

For each Dosing Period, blood samples for PK analysis will be collected on Day 1 (before the morning and evening doses [0 and 12hr]), Day 2 (before the morning and evening doses [24 and 36hr]), and Day 3 (predose [48hr] and 10min, 15min, 20min, 30min, 45min, 60min, 75min, 90min, 2hr, 6hr, 9hr, and 12hr postdose). Allowable deviations from these scheduled PK sampling times are provided in Table 8-1 of the protocol. Individual concentration-time data will be listed for the SS by treatment sequence. [All]

Concentration listings will include nominal PK sampling time, actual sampling times relative to dose administration, deviation from nominal time, and concentrations, day, dosing period and sequence, formulation (tablet or dry syrup).

Plasma concentration data will be listed and summarized with the descriptive statistics by BRV formulation (tablet or dry syrup) and scheduled time for the PKS. [All]

Descriptive statistics will include number of study participants (N), number of available observations (n), mean, standard deviation, median, minimum, and maximum, geometric mean, geometric coefficient of variation (CV), and 95% confidence interval (CI) for the geometric mean.

The geoCV will be calculated as  $geoCV(\%) = 100 \times \sqrt{\exp\{(lnSD)^2\}} - 1$ , where  $lnSD$  is the standard deviation of the log transformed values.

Graphical displays of geometric mean concentrations with its corresponding 95% CI (linear scale and semi-logarithmic scale) on Day 1 to Day 3 and zoomed geometric mean concentrations between 0 and 6 hr on Day 3 will also be presented by BRV formulation (tablet or dry syrup) and scheduled time on semi-logarithmic and linear scales for the PKS. [IA-DMC, All]

Graphical displays of individual plasma concentrations by actual time will be presented on semi-logarithmic and linear scales.

Plasma concentrations will be displayed superimposed in a single plot for both formulations for the PKS. [All]

Spaghetti plots will be presented on Day 3 up to 12 h post-dose separately for BRV formulation, with profiles for all participants superimposed on the same graph for the PKS. [All]

Refer to [Appendix 12](#) (Section 6.12) for standard reporting procedures of individual values and descriptive statistics for plasma concentration data in listings, tables, and figures.

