#### 4.6.1.1.2 Derivation of primary/ other pharmacokinetic variables and descriptive summaries

Pharmacokinetic parameters will be calculated by non-compartmental analysis methods from the concentration-time data using Phoenix® WinNonlin® (Version 8.2 or higher).

Actual sampling times will be used for deriving the PK parameters. Pharmacokinetic parameters will be estimated according to the guidelines presented in [Appendix 13](#), Section 6.13.

$C_{max,ss}$ ,  $AUC_{tau}$ ,  $CL_{ss}/F$ ,  $t_{max,ss}$  and  $C_{trough}$  will be listed by participant and summarized with descriptive statistics by BRV formulation (tablet or dry syrup) for the PKS. [IA-DMC, All]

For individual  $C_{max,ss}$  and  $AUC_{tau}$ , ratio of Test (dry syrup) versus Reference (tablet) will be listed by participant and summarized with descriptive statistics for the PKS. [All]

The ratios between the  $C_{trough}$  after the last dose on Day 3 and the pre-dose concentration before each dose with the exclusion of morning dose on Day 1 ( $R_{trough}$ ) will be listed by participant and summarized with descriptive statistics for the PKS. [All]

For  $t_{max,ss}$ , a distribution-free 90% CI using Hodges-Lehmann's method will be calculated for the median differences (location shift) between each Test (dry syrup) and the Reference (tablet). Median and the corresponding 90% CI for each treatment (tablet or dry syrup) will be provided using cumulative binomial probability. If the exact Hodges-Lehmann confidence limits cannot be calculated, asymmetric limits will be derived instead of symmetric limits. [All]

In addition, all individual PK parameters will be listed by formulation (tablet or dry syrup) for the SS. [All]

The following descriptive statistics will be calculated: mean, SD, geometric mean, geometric coefficient of variation (CV), minimum, median and maximum and 95% confidence interval (CI) for the geometric mean. The only exception is  $t_{max,ss}$ , for which only median, minimum, and maximum will be reported.

Ping pong plots for individual data in the PK parameters ( $C_{max,ss}$  and  $AUC_{tau}$ ) will also be displayed for the PKS. [All]

Refer to [Appendix 12](#) (Section 6.12.2) for standard reporting procedures of individual values and descriptive statistics for PK parameters in listings and tables.

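### Does the exclusion for two or more missing PK samples need to say which of the 17 samples per Dosing Period count?

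*SAP*

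**What the plan says.** SAP 3.4 first admits participants who have a "sufficient number of bioanalytical assessments to calculate reliable estimates for the primary PK parameters" for both formulations. It then lists exclusions by period: carry-over above 5% of Cmax,ss, early vomiting, and missing samples. The missing-sample rule has two limbs. A period is dropped if one PK sample is missing and Cmax,ss "is the sample immediately preceding or following the missing sample or (2) 2 or more samples are missing".

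The sampling schedule is in SAP 4.6.1.1.1. Day 1 has samples at 0 and 12 h. The next entry is "Day 2 (before the morning and evening doses [24 and 36hr". Day 3 has a predose sample and 12 postdose samples up to 12 h. The 12, 24 and 36 h samples feed the concentration summaries and Rtrough, which SAP 4.6.1.1.2 defines as the ratio of the last trough to "the pre-dose concentration before each dose with the exclusion of morning dose on Day 1". The Day 1 predose sample feeds the 5% carry-over check.

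The protocol has no missing-sample rule of its own. Protocol 9.6 says only: "Handling of missing data will be detailed in the SAP". Protocol 9.5 sets a Data Evaluation Meeting for each cohort before database lock, which helps in "guiding decisions on how to manage data issues on a case-by-case basis".

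**The concern.** The second limb does not say which samples are counted. Taken word for word it covers all 17, so losing the 24 h and 36 h samples would remove a period in which both primary parameters are fully measured. One lost Day 2 sample plus one Day 3 sample well away from the peak would have the same effect. Read as a Day 3 rule, neither case leads to exclusion.

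The rule decides which data enter the primary bioequivalence test. The study is open-label, PK parameters may be available when the PKS is defined, and SAP 4.2.3 plans no sensitivity analysis. An unstated scope could in principle be settled differently at the interim and final analyses.

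A related gap is that nothing is said about a missing Day 1 predose sample. If it is the only one missing, neither limb applies and the carry-over check cannot be made.

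**Working it through.** **Sample count (SAP 4.6.1.1.1).** 2 (Day 1) + 2 (Day 2) + 13 (Day 3) = 17 per period. Of the 17 × 16 / 2 = 136 possible missing pairs:

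- both on Days 1–2: 4 × 3 / 2 = 6, Day 3 complete;
- one on each side: 4 × 13 = 52, Day 3 has 12 of 13;
- both on Day 3: 13 × 12 / 2 = 78, excluded under either reading.

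The readings therefore disagree on 6 + 52 = 58 pairs.

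**How often this happens.** The documents give no missing rate, so a per-sample rate q of 0.5%, 1% or 2%, independent across samples, is assumed. P(≥2 of n missing) = 1 − (1−q)^n − nq(1−q)^(n−1). Cohort 1 has 60 × 2 = 120 periods.

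| Expected periods out of 120 | q = 0.5% | q = 1% | q = 2% |
|---|---|---|---|
| Excluded, all 17 samples count | 0.39 | 1.48 | 5.35 |
| Excluded, only Day 3 counts (n = 13) | 0.23 | 0.87 | 3.23 |
| Difference | 0.16 | 0.61 | 2.12 |
| Of which Day 3 is complete | 0.017 | 0.062 | 0.216 |

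The fourth row is 120 × (1−q)^13 × P(≥2 of 4 missing). The difference shrinks further because the first limb already removes some of these periods. If it catches 3 of the 13 Day 3 positions (the peak and its two neighbours, an assumption), the differences become 0.13, 0.48 and 1.68.

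**Effect on power.** Inputs from SAP 5: GMR 0.89, intraparticipant SD 0.183, one-sided alpha 0.03817, 60 evaluable. For the 2×2 crossover on the log scale, SE = 0.183 × √(2/60) = 0.0334, with 58 degrees of freedom. The distance to the lower limit is ln 0.89 − ln 0.80 = −0.1165 + 0.2231 = 0.1066, or 3.19 SE. The exact two one-sided tests calculation, integrating over the sampling distribution of the SD, gives 91.5%. This reproduces the plan's figure of approximately 91%.

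Losing two participants entirely (N = 58) gives 90.7%. That is harsher than losing about two single periods, because SAP 4.2.2 keeps the other period in the mixed model.

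**Missing Day 1 predose sample.** Protocol 2 states: "The plasma half-life of BRV is approximately 9hr in healthy adults". SAP 1.2 sets the wash-out as a "minimum of 6 days and preferably no more than 10 days between the final dose in Dosing Period 1" and the first dose of Dosing Period 2. Six days is 144 h, and 144 / 9 = 16 half-lives. The fraction left is 2^−16, about 0.0015%, against a 5% limit. Reaching 5% after 144 h would need a half-life of 144 / log2(20) ≈ 33 h. Dosing Period 1 has no earlier study dose to carry over, so only the 60 second periods matter: 60q = 0.3 to 1.2 periods expected without a check.

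**The case for a change.** The best case for a change is that the authors named days where they meant them. The carry-over rule just above says Day 1 and Day 3 explicitly, and the second limb says neither. The first limb is tied to Day 3 only because it mentions Cmax,ss. A broader scope could even be deliberate, since both primary endpoints are steady-state quantities and the plan uses the earlier troughs for Rtrough. No other section narrows the rule, and a participant left with one period adds little to a within-participant contrast. A few words would close the gap.

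It stands that the text does not state the scope and that a Day 3 intent has to be inferred. The argument from discretion is weaker. Whether a sample was drawn is an objective fact, and the Data Evaluation Meeting precedes database lock and documents its decisions. PK parameters are needed anyway to apply the first limb, the 5% rule and the vomiting rule, so tighter wording here would not keep them out of view. Nor is it an inconsistency that a specific exclusion removes data which could otherwise be estimated; the vomiting rule can do the same.

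The size argument also points to no change. Dosing and sampling are supervised in the clinic. A participant who withdraws during Days 1 or 2 loses Day 3 as well and is excluded under both readings. The 2% rate is hard to square with the plan: on 17 samples it would cost 1 − (1 − 0.0446)² = 8.7% of participants at least one period, against a total allowance of about 5% for dropout and nonevaluable participants. In addition, the 60 is already net of that allowance, so the 90.7% counts some losses twice.

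**Conclusion.** This is a drafting gap that analysts can fill sensibly. The inclusion sentence and the first limb make Day 3 the natural scope. If the literal count were used instead, the primary data set would differ by roughly 0.2 to 2.1 of 120 periods, and interim power would stay above the planned 90%. The missing Day 1 predose case changes no result, because expected carry-over is negligible after 16 half-lives.

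These sizes rest on assumed missing rates of 0.5% to 2%, on independence between samples, and on the plan's own GMR and SD. The 2% end is probably too high. The only gain from rewording would be a rule fixed in advance, and the validity of the bioequivalence test does not depend on it. No change to the plan is called for.

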## 4 STATISTICAL ANALYSES

### 4.1 General considerations

Statistical analysis and generation of tables, figures, and data listings will be performed using SAS Version 9.4 or higher.

A complete set of listings containing both all documented data and all calculated data will be generated. Missing data will not be imputed.

For categorical endpoints, the number and percentage of participants in each category will be presented. The denominator for percentages will be based on the number of participants appropriate for the purpose of the analysis. For continuous endpoints, descriptive statistics will include number of participants, mean, standard deviation (SD), median, minimum, and maximum. The descriptive statistics for plasma concentrations and PK parameters will be described in [Section 4.6.1.1.1](#) and [Section 4.6.1.1.2](#).

For summaries of demographics and Baseline characteristics: summarize percentages based on all participants in the analysis set and include a potential "Missing" category (corresponding to participants with missing data at the time of the variable being summarized) as the last row in the list of categories being summarized.

Percentages will be presented to 1 decimal place. If the percentage is 100%, no decimal will be presented. If the percentage is 0, no percentage will be presented. Typically, the unit (%) should be presented in the column header, but not with each individual value.

Decimal places for descriptive statistics will always apply the following rules, unless otherwise stated:

- "n" will be an integer

- Mean, SD, and median will use one additional decimal place compared to the original data
- CV [%] will be presented with one decimal place
- Minimum and maximum will have the same number of decimal places as the original value

Derived variables in general will display the mean, SD and median to 1 more decimal place than the variables used in the derivation. If the number of decimal places reported in the raw data is varied then use either the maximum raw number of reported decimal places or 3, whichever is the lowest, as a guide for the descriptive statistics.

If participants have more than one observation for a given time point, the observation closest to the intended time point will be used. If both observations are equidistant from the intended time point, then the later value will be used.

Standard reporting procedures of PK concentrations and parameters in listings, tables, and figures are described in [Appendix 12](#) (Section 6.12).

The analysis outputs prepared as Interim Analyses (IA) for DMC (IA-DMC), All Analyses (All) are indicated as follows:

- IA-DMC will be performed at IA for DMC after Cohort 1 is completed.
- All analyses will be performed either at IA after Cohort 1 is completed or Final Analyses (FA) after Cohort 2 is completed. If bioequivalence (BE) or futility is confirmed by DMC at IA and the study is terminated at IA early after Cohort 1 is completed, the IA (All) will be performed at IA. Otherwise, the FA will be performed after Cohort 2 is completed.

TLF shells will clarify “Interim Analyses (DMC)”, “Interim Analyses (All)” or “Final Analyses”.

#### **4.1.1 Analysis time points**

##### **4.1.1.1 Relative day for listings**

Relative day will be derived with the date of the first IMP administration in each Dosing Period as reference for that specific Dosing Period.

###### For days on the day of IMP administration in each Dosing Period

Relative day will be calculated as follows:

Relative day = Current date - Date of the first IMP administration + 1  
i.e., the day of the first IMP administration in each Dosing Period will have a relative day of ‘1’.

###### For days prior to IMP administration in each Dosing Period

Relative day will be prefixed with ‘-’ and calculated as follows:

### Relative day

= Current date – Date of the first IMP administration within the same Dosing Period  
e.g., the day prior to the first IMP administration will have a relative day of ‘-1’.

#### For days prior to the first IMP administration in the Screening Period

Relative day will be prefixed with ‘-’ and calculated as follows:

Relative day = Current date – Date of the first IMP administration  
e.g., Screening Visit that is 7 days prior to the first IMP administration will have a relative day of ‘-7’.

#### For days after the day of the last IMP administration in Dosing Period

Relative day will be prefixed with ‘+’ and will be calculated as follows:

Relative day = Current date – Date of the last IMP administration within the same Dosing Period  
e.g., the day after the last IMP administration in a Dosing Period will have a relative day of ‘+1’.

#### For days after the Dosing Period

Relative day will be prefixed with ‘+’ and calculated as follows:

Relative day = Current date – Date of the last IMP administration  
e.g., A certain day in a washout period following Dosing Period 1 that is 7 days after IMP administration in Dosing Period 1 will have a relative day of ‘+7’.  
e.g., Safety Follow-Up Visit that is 8 days after the last IMP administration will have a relative day of ‘+8’.

Relative day will not be calculated for partial dates. Relative day for partial days will be displayed as ‘--’ to distinguish it from missing values which are displayed as blanks.

#### **4.1.1.2 Analysis periods**

The total duration of the study for an individual study participant is 21 days to 53 days and will include:

- A Screening Period (2 to 28 days before IMP administration)
- Two Dosing Periods (5 days each, with IMP administration on Day 1 and Day 2 (morning and evening doses 12 hours apart), and Day 3 (morning dose only) of each Dosing Period)
- A Wash-out Period following Dosing Period 1 (minimum of 6 days and preferably no more than 10 days between the final dose in Dosing Period 1 and the first dose in Dosing Period 2 for each participant)
- An SFU Visit/Withdrawal Visit (7 to 9 days after the last IMP administration)

